## **4.2. Measures Taken to Avoid Bias**

Subjects will be randomized in a 1:1 ratio to receive itacitinib plus corticosteroids or matching placebo plus corticosteroids and will be stratified by GVHD risk status (ie, standard-risk versus high-risk; [MacMillan et al 2015](#); [Appendix C](#)). Centralized randomization numbers within each stratum will be created for treatment assignment. Subjects, investigators, and the study team will be blinded to treatment assignment. A sponsor statistician who is not part of the study team will be unblinded and may provide summary aggregated data by treatment cohort to the sponsor and/or the DMC, but individual subject data will remain blinded.

Disease assessments and safety assessments will be performed in accordance with standardized criteria.

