##### **5.1.2. Randomization and Blinding**

Randomization will occur centrally by IVRS. Full instructions will be provided in the IVRS manual. Randomization will be stratified by standard risk and high risk ([MacMillan et al 2015](#);

[Appendix C](#)) at a ratio of 1:1. As this is a randomized, double-blind, placebo-controlled study, neither investigators, nor the sponsor will be aware of the treatment cohort to which the subject is randomized.

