**Table 8: Operation Characteristics Using Hwang-Shih-DeCani Alpha Spending Function with Shape Parameter -4**

		No. of Subjects (%)	Alpha Spent / Cumulative	Efficacy Boundary or Critical Value (as Compared With Observed Normalized Test Statistic z)
ORR at Day 28	Interim 1	112 (25.7)	–	–
	Interim 2	360 (82.6)	0.0122/0.0122	2.249810
	Final	436 (100)	0.0128/0.025	2.015483

The interim analyses will be performed by an independent statistician and programmer not involved with the conduct of the study as described in the DMC charter.

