An independent DMC will be charged with evaluating interim results. The DMC will consist of clinicians and an independent statistician. The sponsor will remain blinded, and DMC decisions will be communicated through sponsor management as dictated in the DMC charter. Additional operational details of the interim analyses, including tables, figures, and listings provided to the DMC, will be provided in the DMC Charter.

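### Protocol 4.2 lets an unblinded sponsor statistician give by-arm summaries to the sponsor, not only after final unblinding, which conflicts with the sponsor blind in SAP 9.1.2

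*Protocol*

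**What the plan says.** Protocol 4.2 blinds three parties: "Subjects, investigators, and the study team will be blinded to treatment assignment". It then makes an exception: a sponsor statistician outside the study team "will be unblinded and may provide summary aggregated data by treatment cohort to the sponsor and/or the DMC". The permitted recipients are the sponsor, the DMC or both. The safeguard attached to the release covers subject-level data only: "but individual subject data will remain blinded".

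Other sections describe a blinded sponsor.

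- Protocol 5.1.2: "neither investigators, nor the sponsor will be aware of the treatment cohort to which the subject is randomized". SAP 3.1 repeats this. Neither gives an exception.
- End of SAP 9.1.2: "The sponsor will remain blinded, and DMC decisions will be communicated through sponsor management as dictated in the DMC charter".
- Protocol 9.2.2, below Table 8: "The interim analyses will be performed by an independent statistician and programmer not involved with the conduct of the study". SAP 3.4.2 says the same.
- Protocol 9.6: the independent statistician gives the second-interim results to the DMC statistician, who with the DMC chair makes a recommendation to the sponsor.
- Protocol 8.7: the DMC works autonomously from sponsor personnel.

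SAP 10.1, which lists changes to protocol-defined analyses, does not reconcile these statements.

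**The concern.** A summary of Day 28 response or nonrelapse mortality (NRM) by treatment arm is the estimated treatment effect. Keeping each subject's assignment hidden does not keep that effect hidden from whoever holds the summary.

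The sponsor makes plan-level decisions while the trial runs. The futility rule is nonbinding and leaves the sponsor to weigh the totality of evidence (Protocol 9.2.1, SAP 3.4.1). The sponsor also amends the SAP. Amendment 1 is dated 23 JUL 2019. It changed how type I error is controlled for the key secondary endpoint, and refined the definition and analysis of Month 6 NRM (SAP 10.2.1). The Interim 2 cutoff had already passed, on 17 APR 2019 (SAP 5.3.2).

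If by-arm data may reach the sponsor, the protocol alone cannot show that such decisions were independent of the observed effect.

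**Working it through.** There is no sample size, power or alpha figure to reproduce. The check sets the blinding statements side by side.

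| Source | Who is unblinded or does the interim work | What may reach the sponsor | Timing limit |
|---|---|---|---|
| Protocol 4.2 | A sponsor statistician outside the study team | Summaries by arm | None stated |
| Protocol 5.1.2, SAP 3.1 | No exception given | Not a subject's assignment | None stated |
| Protocol 9.2.2, SAP 3.4.2 | Independent statistician and programmer | Not addressed | At the interims |
| Protocol 9.6 | Independent statistician, then DMC statistician | A recommendation | Second interim |
| SAP 9.1.2 | Independent DMC evaluates the results | DMC decisions; sponsor stays blinded | At the interims |

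**Step 1: 4.2 against SAP 9.1.2.** A sponsor that holds by-arm summaries is not blind to the comparison. One section permits what the other excludes. This conflict is direct.

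**Step 2: 4.2 against Protocol 9.2.2 and 9.6.** The later sections set a route from an independent statistician to the DMC statistician, with a recommendation to the sponsor. Section 4.2 opens a second route, from a sponsor statistician to the sponsor. The documents do not say whether the two statisticians are the same person. If they are, the sponsor is still a permitted recipient under 4.2.

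**Step 3: 4.2 against Protocol 5.1.2 and SAP 3.1.** These sections concern the arm to which a given subject is randomized. By-arm aggregates do not reveal that, so the release itself does not contradict them. What does is that a sponsor statistician is unblinded, while both sections say without qualification that the sponsor is unaware of assignment. This conflict is narrower.

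**Step 4: timing.** Section 4.2 gives none. It pairs the sponsor with the DMC as recipients and says that individual data will stay blinded. Both features fit a trial still in progress, and nothing confines the release to the period after final unblinding.

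**Step 5: which decisions are exposed.** To favour one arm in a case-level approval, the sponsor would need to know the subject's arm, and an aggregate does not show it. Plan-level decisions need only the aggregate.

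**Step 6: dates.** From 17 APR 2019 to 23 JUL 2019 is 13 + 31 + 30 + 23 = 97 days. This runs from the data cutoff. The documents do not date any unblinding of the interim data.

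**The case against.** The strongest defence is that 4.2 is a general sentence governed by the specific interim rules in Protocol 9.2.2, 9.6 and 8.7 and the later SAP 9.1.2. On this reading the release to the sponsor belongs to the primary analysis: the sponsor runs the final analyses (SAP 9.2) while some subjects are still on treatment (Protocol 4.5), so aggregates could be shared while individual codes stay closed. The DMC charter, which is not among the documents, may also contain a firewall. This is a fair account of what may have been intended. It does not remove the conflict, because 4.2 states no such limit and neither cites the charter nor makes release subject to it.

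Two stronger readings are tempting, and the documents support neither.

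- **A reader might infer that case-level conduct is open to bias,** for example sponsor approval of early tapers or longer dose delays, or the grading of response. Section 4.2 keeps subjects, investigators and the study team blinded, and subject-level data too. Investigators grade response (Protocol 7.6.1). Where Protocol 8.4 deals with continuation after unblinding, that subject's arm is already known, so an aggregate adds nothing.
- **A reader might infer that SAP Amendment 1 was shaped by interim results.** The wording of 4.2 is permissive, and no release is recorded. SAP 10.2.1 attributes the NRM definition and analysis change to Health Authority feedback. It gives no reason for the alpha change, but that change mostly made the NRM test stricter. The level is now 0.0125, against about 0.0219 at the final analysis if NRM had taken the response level in SAP Table 2. At the interim sizes in SAP Appendix D (410 to 435 subjects), the response boundaries correspond to about 0.020 to 0.025. Only at the projected 360 subjects is 0.0125 slightly looser, against 0.0122.

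**Conclusion.** The concern holds as a contradiction within the plan. Protocol 4.2 permits by-arm summaries to go to the sponsor before final unblinding. SAP 9.1.2 says the sponsor stays blinded, and Protocol 9.2.2 and 9.6 set a different route. The conflict with Protocol 5.1.2 and SAP 3.1 is limited to the sponsor statistician's access to the codes.

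The effect on error rates or estimates cannot be sized, because it depends on whether data were released and used. What is exposed is the independence of the futility decisions and of SAP amendments. The finding does not extend to case-level approvals, and it does not say that a release occurred. It is still more than a missing detail, because the protocol's own section on avoiding bias grants the permission.

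It rests on two assumptions: that 4.2 applies before final unblinding, since it says nothing to the contrary, and that no document outside those reviewed overrides it.

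**What to change.** In Protocol 4.2, delete the sponsor as a recipient of by-arm summaries, leaving the DMC only. Assign their preparation to the independent statistician and programmer already named in 9.2.2. Removing the recipient alone is not enough, because it would leave a sponsor statistician unblinded.

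State that the sponsor receives only the DMC recommendation until the database is locked and unblinded for the final analysis, or until a decision to stop at an interim is made. The second condition is needed because SAP 6 provides for a stop at Interim 1 or 2. Align Protocol 5.1.2 and SAP 3.1 with the revised text.

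The cost is a few sentences in a protocol amendment and a matching SAP edit. No new staff are needed, since the independent statistician and programmer are already planned. The small downside is that the sponsor gives up by-arm aggregate views before that point.

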## **4.3. Number of Subjects**

### **4.3.1. Planned Number of Subjects**

This study will enroll approximately 218 subjects with clinically or pathologically confirmed Grade II to IV aGVHD per treatment cohort, for a total of 436 subjects at approximately 85 study sites.

### **4.3.2. Replacement of Subjects**

Not applicable.

## **4.4. Duration of Treatment and Subject Participation**

After signing the ICF, screening assessments may be completed over a period of up to 28 days. Each subject enrolled in the study may continue to receive study treatment as long as benefit is being observed and/or treatment withdrawal criteria are not met. If the subject discontinues study treatment, the treatment period will end, and the subject will enter the follow-up period (see [Section 6.4](#)). The safety follow-up period will last 30 to 35 days, and the survival follow-up period will last until death or study withdrawal. Study participation is expected to average approximately 12 months per individual subject but may vary based on clinical outcomes.

## **4.5. Overall Study Duration**

The study begins when the first subject signs the informed consent. Subjects who are still on-study at the time of the primary endpoint analysis will continue to receive study treatment until treatment withdrawal criteria are met ([Section 5.5](#)). All subjects will be followed for survival until death, withdrawal of consent, or the end of the study, whichever occurs first. The study will end once 75% of subjects have died or are lost to follow-up. Provisions will be made

to ensure access to treatment for subjects who are continuing to benefit from study treatment at the time of study completion.

#### **4.6. Study Termination**

The investigator retains the right to terminate study participation at any time, according to the terms specified in the study contract. The investigator is to notify the institutional review board (IRB)/independent ethics committee (IEC) in writing of the study's completion or early termination, send a copy of the notification to the sponsor or sponsor's designee, and retain 1 copy for the site study regulatory file.

The sponsor may terminate the study electively, if required by regulatory decision, or upon advice of the DMC. If the study is terminated prematurely, the sponsor will notify the investigators, the IRBs and IECs, and the regulatory bodies of the decision and reason for termination of the study. The DMC will recommend termination of the study if warranted, as described in Section 8.7.

### **5. TREATMENT**

#### **5.1. Study Drug and Treatment Assignment**

##### **5.1.1. Subject Numbering and Treatment Assignment**

Each subject will be identified in the study by a subject ID number, which is a combination of the site ID and subject number. Site staff should contact the IVRS to obtain the subject ID number during screening.

Site staff will contact the IVRS to randomize the subject and obtain the initial study drug assignment. The investigator or designee will select the assigned bottles of study drug from their stock that correspond to the number provided by the IVRS, record the bottle numbers in the eCRF, and dispense the study drug to the subject. All subsequent dispensing of study drug should follow this process. Full details will be provided in the IVRS manual.

All subject numbers will be 6 digits; the first 3 digits will be the site number and the last 3 digits will be the subject's number. This subject number will be maintained throughout the study and will not be reassigned. Subjects who withdraw consent or discontinue from the study after being assigned a subject number will retain their initial number.

If a subject is mistakenly given a bottle of study drug that is not the bottle assigned by the IVRS, then the IVRS help desk must be notified immediately. The reason for the misallocation of the study drug must be documented by the study site.

For subjects who signed an ICF but are not allocated and for subjects who are allocated but were not treated, refer to the eCRF Completion Guidelines for instruction on which eCRFs to complete.

##### **5.1.2. Randomization and Blinding**

Randomization will occur centrally by IVRS. Full instructions will be provided in the IVRS manual. Randomization will be stratified by standard risk and high risk ([MacMillan et al 2015](#);

[Appendix C](#)) at a ratio of 1:1. As this is a randomized, double-blind, placebo-controlled study, neither investigators, nor the sponsor will be aware of the treatment cohort to which the subject is randomized.

## **5.2. Study Drugs**

### **5.2.1. Itacitinib/Placebo**

#### **5.2.1.1. Description and Administration**

Itacitinib 100 mg (free base equivalent) sustained-release tablets contain the active ingredient, hypromellose, microcrystalline cellulose, lactose monohydrate, and magnesium stearate.

Placebo tablets developed to match the itacitinib 100 mg sustained-release tablets are similar in appearance to active drug product tablets with regard to color, size, and shape and contain hypromellose, microcrystalline cellulose, and magnesium stearate.

Itacitinib or placebo will be administered PO at a starting dose of 200 mg QD (2 × 100 mg tablets).

Subjects may have dose reductions or modifications of itacitinib or placebo during the course of treatment based on AEs, clinical evaluation, and laboratory assessments. See [Section 5.4](#) for dose modifications of study drug.

Subjects are permitted to remain on itacitinib or placebo treatment until withdrawal from study treatment is considered necessary as per [Section 5.5](#).

#### **5.2.1.2. Supply, Packaging, and Labeling**

Itacitinib or placebo tablets will be provided to sites in high-density polyethylene bottles as applicable by Incyte. No preparation is required.

All Incyte investigational product labels will be in the local language and will comply with the legal requirements of each country.

#### **5.2.1.3. Storage**

Itacitinib or placebo should be stored at ambient conditions (15°C to 30°C, or 59°F to 86°F) as per the [IB](#).

#### **5.2.1.4. Instruction to Subjects for Handling Itacitinib or Placebo**

The subject must be instructed in the handling of itacitinib or placebo as follows:

- To store the bottles at room temperature, in a safe place and out of the reach of children.
- To only remove the number of tablets needed at the time of administration.
- Not to remove tablets in advance of the next scheduled administration.
- To make every effort to take doses on schedule.
- To report any missed doses.

- To take tablets with a glass of water.
- Not to take another dose if vomiting occurs after taking study medication.
- To refrain from taking study medication on the day of clinic visits until after blood samples are collected.
- To fast on PK assessment days (Days 1, 7, and 28).
- To bring all used and unused bottles of study medication to the site at each visit.

### **5.2.2. Corticosteroids**

Either oral prednisone or intravenous methylprednisolone may be used to begin standard corticosteroid background treatment at the investigator's discretion.

#### **5.2.2.1. Prednisone**

##### **5.2.2.1.1. Description**

Prednisone is a white to off-white, odorless, crystalline powder. Tablets are typically white in color and contain lactose monohydrate, magnesium stearate, microcrystalline cellulose, pregelatinized starch, and sodium starch glycolate. Commonly available dose strengths include 1 mg, 2.5 mg, 5 mg, 10 mg, 20 mg, and 50 mg tablets.

##### **5.2.2.1.2. Supply, Packaging, and Labeling**

Investigators are responsible for ensuring that subjects receive commercially available supplies of prednisone for the duration of the study treatment period. Incyte may provide prednisone where required by applicable law or regulation.

##### **5.2.2.1.3. Storage**

Prednisone tablets should be stored in accordance with local prescribing information requirements.

#### **5.2.2.2. Methylprednisolone**

##### **5.2.2.2.1. Description**

Methylprednisolone sterile powder is an anti-inflammatory glucocorticoid, which contains methylprednisolone sodium succinate as the active ingredient. Methylprednisolone sodium succinate, USP, is the sodium succinate ester of methylprednisolone, and it occurs as a white, or nearly white, odorless hygroscopic, amorphous solid. It is very soluble in water and in alcohol; it is insoluble in chloroform and is very slightly soluble in acetone.

##### **5.2.2.2.2. Supply, Packaging, and Labeling**

Investigators are responsible for ensuring that subjects receive commercially available supplies of methylprednisolone for the duration of the study treatment period. Incyte may provide methylprednisolone where required by applicable law or regulation.

#### **5.2.2.2.3. Storage**

Methylprednisolone (unreconstituted product or solution) should be stored in accordance with local prescribing information.

#### **5.2.3. Starting Dose and Administration of Corticosteroids**

All subjects will receive methylprednisolone 2 mg/kg IV daily (or prednisone equivalent) or at a dose that is appropriate for the severity of disease as outlined per local treatment guidelines ([Martin et al 2012](#), [Ruutu et al 2014](#)) as background treatment. Subjects who previously began corticosteroid therapy at a different dose may remain on that dose if considered clinically appropriate by the treating physician. Corticosteroids should be tapered as per institutional guidelines at a rate that is commensurate with resolution of GVHD manifestations.

If GVHD flares during the taper of prednisone or methylprednisolone, the dose may be re-escalated at the investigator's discretion and will not be considered treatment failure, as long as the dose does not exceed the initial starting dose. If the dose required exceeds this threshold, or if the flare is not responsive to increased corticosteroids or multiple flares are observed, then the subject will be considered to have experienced treatment failure and be withdrawn from study treatment.

#### **5.2.4. Prophylactic and Supportive Care Medications**

Patients who undergo allo-HSCT are at risk for a variety of infections based on the degree of immunosuppression induced by the conditioning regimen before transplant. As such, it is considered routine practice to use antibiotics, anti-infectives, and immunizations as prophylactic therapies ([Tomblyn et al 2009](#)). In cases where post-transplant anti-infective prophylaxis measures are necessary, ongoing therapy may continue at the investigator's discretion per institutional guidelines.

Systemic and topical GVHD prophylaxis medications (eg, cyclosporine, methotrexate, and tacrolimus) may be continued at therapeutic doses as appropriate based on stage and sites of disease.

Additional supportive care measures (eg, use of antimotility agents for diarrhea management, topical steroids, beclomethasone, budesonide, ursodiol) are permitted at the investigator's discretion.

See Section [5.5.4](#) for additional details.

### **5.3. Treatment Compliance**

Treatment compliance with all study-related medications should be emphasized to the subject by the site personnel, and appropriate steps should be taken to optimize compliance during the study. Itacitinib or placebo compliance will be calculated, by the sponsor, based on the drug accountability documented by the site staff and monitored by the sponsor/designee (tablet counts). Subjects will be instructed to bring all study-related medications with them to each study visit in order for site personnel to conduct tablet counts to assess study drug accountability. The drug accountability documentation will be used by the sponsor to calculate treatment compliance.

Although commercial supplies of corticosteroids will be used, dose changes and interruptions will also be documented in the medical record and monitored by the sponsor or its designee. As corticosteroid dose strengths and administration types will vary, compliance with corticosteroids will not be calculated.

## **5.4. Treatment Interruptions and Adjustments**

### **5.4.1. Dose Modifications**

Dose interruptions and modifications may occur for individual study subjects based on the emergence or resolution of toxicity.

### **5.4.2. Criteria and Procedures for Dose Interruptions and Adjustments of Study Drug**

Treatment with itacitinib/placebo may be delayed up to 14 days to allow for resolution of toxicity. After interruption, subjects should be evaluated on a weekly basis until resolution/improvement of the AE. Subjects may resume treatment if no medical condition or other circumstance exists that, in the opinion of the investigator, would make the subject unsuitable for further participation in the study. The investigator should contact the medical monitor to discuss cases where treatment has been delayed for more than 14 days before restarting treatment.

Because subjects may enter the study with compromised bone marrow function, these dose reductions are provided as guidelines (see [Table 1](#) and [Table 2](#)); individual decisions regarding dose reduction should be made using clinical judgment and an individual benefit/risk assessment, taking into account relatedness of the AE to the study drug and the subject's underlying condition. Adverse events that have a clear alternative explanation or transient ( $\leq 72$  hours) abnormal laboratory values without associated clinically significant signs or symptoms may be exempt from dose-reduction rules. The sponsor's medical monitor may be consulted for advice.

Subjects receiving itacitinib/placebo at a dose of 200 mg QD may have their dose reduced to 100 mg QD. Subjects who are unable to tolerate itacitinib/placebo at a dose of 100 mg QD should be withdrawn from study treatment.

